#### **5.2.1.2.1 Dose Modifications and Decisions After Interim Reviews**

At the time of this protocol amendment (-02), enrollment into Cohorts 1 through 4 has been completed. As planned, protocol-defined interim reviews of safety and PK data were completed for the first 50% of subjects in each age cohort. The dose modifications that were made as a result of the interim reviews are shown in [Figure 2](#). These dose modifications were communicated to sites via Protocol Clarification Letters and are based on the following considerations:

[figure not shown]
- At time of enrolling Cohorts 1 through 3, no pediatric-specific population PK model for imipenem and REL was available; therefore, PK endpoints from these cohorts were estimated based on an allometrically-scaled adult population PK model. The interim reviews in each cohort showed that the scaled adult model appropriately described the observed imipenem and REL concentrations from pediatric subjects in Cohorts 1 through 3.
- Cohort 1: At the initial dosing guidance of 15/7.5 mg/kg IMI/REL as a 30-minute IV infusion, all subjects received the full adult dose of 500/250 mg IMI/REL based on their weight. Based on modeling, likely weights of subjects in the age cohort would almost always necessitate the full 500/250 mg dose of IMI/REL; therefore, the dosing regimen was simplified to a flat single dose of 500/250 mg IMI/REL administered as a 30-minute IV infusion for the remaining subjects of Cohort 1.
- Cohort 2: Simulations showed that by increasing the study drug infusion duration from 30 minutes to 60 minutes at the proposed initial dose of 15/7.5 mg/kg IMI/REL, >90% of subjects in this age cohort would meet the protocol-defined safety targets, and ~ 75% of subjects in this age cohort would meet PK targets for both imipenem and REL. Therefore, the dosing regimen was changed to 15/7.5 mg/kg IMI/REL as a 60-minute intravenous infusion for the remaining Cohort 2 subjects in order to ensure the majority of patients met the safety and PK targets.
- Cohort 3: Simulations showed that by infusing IMI/REL at 15/7.5 mg/kg over 60 minutes (rather than over 30 minutes), ~98% of subjects in this age cohort would meet the protocol-defined safety targets for both imipenem and REL. Furthermore, a change in the infusion period from 30 minutes to 60 minutes was consistent with the

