updated regimen for the remaining subjects in Cohort 2. Therefore, the dosing regimen was changed to 15/7.5 mg/kg IMI/REL as a 60-minute intravenous infusion for the remaining Cohort 3 subjects.

After completion of enrollment of Cohorts 1 through 3 (2 to <18 years of age), the protocol-defined interim review of aggregate safety and PK data from these 3 cohorts was conducted. The observed safety data for all 19 subjects who received IMI/REL demonstrated an acceptable safety profile. PK data from the 18 PK evaluable subjects were used to develop a pediatric-specific population PK model for imipenem and relebactam. In order to extrapolate the developed pediatric population PK model for the older cohorts (2 to <18 years of age) to Cohorts 4 and 5 (<2 years of age), an adjustment function was included to account for a lack of full renal maturation for the subjects in this age range. Simulations were conducted to project the initial doses for Cohorts 4 and 5. The dosing regimen specified in Table 2 for Cohorts 4 and 5 was selected based on drug exposures that were projected to provide optimal probability of safety and efficacy.

For Cohort 4, simulations from the interim review showed that infusing IMI/REL at 15/7.5 mg/kg (rather than 10/5 mg/kg) over 60 minutes would result in projected efficacy and safety targets similar to the evaluated initial Cohort 4 dose of 10/5 mg/kg. Furthermore, choosing a 15/7.5 mg/kg dose for the remaining 4 subjects enabled data collection over an expanded dosing range, and therefore supports population PK model optimization and future clinical use. Additionally, the 15/7.5 mg/kg dosing regimen of IMI/REL is consistent with the current PRIMAXIN®/TIENAM® (imipenem/cilastatin) dosing recommendations for pediatric patients, for which there is a long history of safe and efficacious use.

Figure 2 Dose Modifications for Cohorts 1, 2, 3, and 4 After Interim Reviews

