### 7.1.3.2 Pharmacokinetic/Pharmacodynamic Evaluations

Four PK samples per subject will be collected in each of the age cohorts as follows:

1. First PK sample: predose sample taken within 30 minutes before the start of study drug infusion.
2. Second PK sample: collected within 10 minutes after the end of study drug infusion.
3. Third PK sample:
  - Cohorts 1 through 4: obtained 1.5 to 2.5 hours after the start of study drug infusion.
  - Cohort 5: obtained 2 to 5 hours after the start of study drug infusion.

4. Fourth PK sample:

- Cohorts 1 through 4: obtained 4.5 to 6 hours after the start of study drug infusion.
- Cohort 5: obtained 6 to 12 hours after the start of study drug infusion.

All PK samples must be drawn within the specified time windows, and the actual sampling times must be documented. This sampling scheme allows for a balance between the maximum coverage of the concentration profile across time required to adequately characterize the PK profile, while maintaining a minimal number of samples per subject.

The following model-based and derived PK parameters will be calculated for REL and/or imipenem, as appropriate:

- $AUC_{0-\infty}$
- $C_{max}$
- %TMIC (imipenem only)
- Systemic clearance (CL)
- Central volume of distribution ( $V_c$ )

The following noncompartmental analysis (NCA)-based PK parameters will be calculated for cilastatin:

- $AUC_{0-\infty}$
- Time to maximum observed plasma drug concentration
- Concentration at end of infusion (CEOI)
- $t_{1/2}$
- CL
- Volume of distribution ( $V_{ss}$ )

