
Modeling and Simulation (M&S) Methods for Key Pharmacokinetic Analyses
	
Pediatric REL and imipenem data will be used to determine pediatric PK parameters by using the previous adult PK model as a starting point. The PK parameters will be continuously updated as pediatric PK data become available from each age cohort. A nonlinear mixed effects modeling approach will be applied for model building.
 
The target is <math>AUC_{0-\infty} \geq 37.5 \mu\text{M}\cdot\text{hr}</math> (and <math>\leq 200 \mu\text{M}\cdot\text{hr}</math>) for REL and <math>TMIC \geq 30\%</math> (and <math>AUC_{0-\infty} \leq 250 \mu\text{M}\cdot\text{hr}</math>) for imipenem. The goal of model-based simulations will be to derive a dosing regimen where these predefined targets are jointly achieved in a proportion of pediatric subjects similarly covered in adults (~90% probability of target attainment) for each age cohort.
 
For cilastatin, descriptive statistics will be provided for PK parameters by age cohort, based on NCA.
 
Details on modeling and simulation (M&S) methods are provided in Section 8.6.1 – Modeling & Simulation Methods for Pharmacokinetic Analyses.

Statistical Methods for Safety Analyses
	
Descriptive statistics will be provided for all safety assessments described above.

Interim Reviews
	
Interim reviews of PK and safety data are planned at 3 stages in the study. Dose modification may be suggested based on interim review results. The planned interim reviews are summarized in Section 8.7 – Interim Review for Potential Dose Adjustment.

Multiplicity
	
No multiplicity adjustment is planned.

Sample Size and Power
	
Based on PK Precision                  Proposed number of study participants by pediatric subset:  Cohort 1 (age 12 to <18 years); at least 6 subjects  Cohort 2 (6 to <12 years); at least 6 subjects  Cohort 3 (2 to <6 years); at least 6 subjects  Cohort 4 (3 months to <2 years); at least 8 subjects, at least 4 of whom are <1 year of age  Cohort 5 (birth to <3 months); at least 18 subjects with at least 6 younger neonates (<1 week age), at least 6 older neonates (1 to <4 weeks age), and at least 6 infants (4 weeks to <3 months)
 
Details on sample size calculation are provided in Section 8.9 – Sample Size and Power Calculations.

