## **8.6 Statistical Methods**

### **8.6.1 Modeling & Simulation Methods for Pharmacokinetic Analyses**

Relebactam and imipenem data will be used to develop a pediatric population PK model by using previous adult data in the form of the adult population PK model, which will be continuously updated as pediatric PK data become available from each age cohort. Any missing postdose plasma concentrations will be treated as missing. Values below the limit of quantification will be assigned a value of zero. A nonlinear mixed effects modeling approach will be used for model building. A Modeling and Simulation Analysis Plan with further details on the methodology will be prepared and finalized before database lock and analysis of the data.

There will be no formal hypothesis testing. The target is  $AUC_{0-\infty} \geq 37.5 \mu\text{M}\cdot\text{hr}$  (and  $\leq 200 \mu\text{M}\cdot\text{hr}$ ) for REL and  $TMIC \geq 30\%$  (and  $AUC_{0-\infty} \leq 250 \mu\text{M}\cdot\text{hr}$ ) for imipenem. The goal of model-based simulations will be to derive a dosing regimen where these targets are jointly achieved in a proportion of pediatric subjects similarly covered in adults (~ 90% probability of target attainment) for each age cohort; hence, achieving these targets implies similar efficacy as that obtained in adults. An absolute (mg) or weight-based (mg/kg) dose, whichever is found most suitable for each age cohort, will be selected based on the simulation results.

For cilastatin, an NCA will be conducted to determine its PK parameters. Descriptive statistics will be provided for cilastatin PK parameters by age cohort.

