### **8.6.2 Statistical Methods for Safety Analyses**

Safety and tolerability will be assessed by clinical review of all relevant parameters including the incidence, severity, and type of AEs, changes in clinical laboratory tests, and changes from baseline in vital sign measurements at the interim reviews and the end of study.

The type and incidence of all AEs and serious adverse events (SAEs) will be tabulated for each age cohort and dose level. The broad clinical and laboratory AE categories consisting of the percentage of subjects with any AE, a drug-related AE, an SAE, a drug-related SAE, and who discontinued due to an AE, as well as the most frequently occurring individual AEs will be summarized in the same manner. Special attention will be given to local tolerability events occurring at time of study drug administration and to those subjects who discontinue due to

an AE or an SAE. Descriptive and/or summary statistics for the raw laboratory safety tests, vital sign measurements, and/or changes from baseline may also be computed, as deemed clinically appropriate.

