## **9.0 LABELING, PACKAGING, STORAGE AND RETURN OF CLINICAL SUPPLIES**

### **9.1 Investigational Product**

The investigator shall take responsibility for and shall take all steps to maintain appropriate records and ensure appropriate supply, storage, handling, distribution and usage of investigational product in accordance with the protocol and any applicable laws and regulations.

Clinical Supplies will be provided by the Sponsor as summarized in [Table 5](#).

Clinical supplies will be packaged to support enrollment and replacement subjects as required. When a replacement subject is required, the Sponsor or designee needs to be contacted prior to dosing the replacement supplies.

Table 5 Product Descriptions

Product Name & Potency	Dosage Form	Source/Additional Information
MK-7655A, MK-7655 250 mg/ Imipenem 500 mg/ Cilastatin 500 mg	Powder for Constitution	Provided centrally by the Sponsor

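### Cilastatin PK is to be summarised by age cohort alone, although Cohort 4 was dosed at two levels and Cohorts 2 and 3 at two infusion durations

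*Combined protocol and SAP*

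**What the plan says.** The layout of the cilastatin results is stated in two places. Section 8.6.1: "Descriptive statistics will be provided for cilastatin PK parameters by age cohort". The summary table in Section 8.1: "For cilastatin, descriptive statistics will be provided for PK parameters by age cohort, based on NCA". Neither splits by dose or infusion duration, and neither mentions dose normalisation. Section 8.4.1 lists AUC0-∞, C_EOI, t1/2, CL and Vss for cilastatin; Section 7.1.3.2 also lists the time of maximum concentration.

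The regimens were not constant within cohorts:

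- **Cohort 4.** Table 2 starts it at 10/5 mg/kg over 60 minutes, with a review after the first four subjects (Section 2.1). Section 5.2.1.2.1 then says that "choosing a 15/7.5 mg/kg dose for the remaining 4 subjects enabled data collection over an expanded dosing range". Section 5.2.2 keeps the infusion at 60 minutes throughout.
- **Cohorts 2 and 3.** Both start at 15/7.5 mg/kg over 30 minutes. For Cohort 2, "the dosing regimen was changed to 15/7.5 mg/kg IMI/REL as a 60-minute intravenous infusion for the remaining Cohort 2 subjects"; Cohort 3 changed in the same way.
- **Cohort 1.** After its review, according to Section 5.2.1.2.1, "the dosing regimen was simplified to a flat single dose of 500/250 mg IMI/REL administered as a 30-minute IV infusion for the remaining subjects". Section 5.2.2 instead gives 60 minutes after the review for Cohorts 1 to 3 together.

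Table 5 (Section 9.1) gives the vial as "MK-7655 250 mg/ Imipenem 500 mg/ Cilastatin 500 mg", so the cilastatin dose equals the imipenem dose. For adverse events the plan does split further: Section 8.6.2 says their type and incidence "will be tabulated for each age cohort and dose level".

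**The concern.** AUC0-∞ and C_EOI depend on dose, and C_EOI and Tmax depend also on infusion duration. A cohort mean taken over two regimens estimates a quantity that belongs to neither, and its standard deviation or CV includes the planned regimen difference as if it were variation between children.

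Cilastatin is named in the primary objective (Section 3.1), its non-model-based endpoints stand under the primary endpoints in Section 8.1, and the noncompartmental analysis is its only planned analysis. What is at stake is how the reported cilastatin exposure can be read, above all in Cohort 4. Target attainment and dose selection do not use cilastatin.

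**Working it through.** The plan gives no numerical figure for the cilastatin summaries, so there is none to reproduce. The check is what pooling does to each parameter.

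**Which parameters are affected.** Under linear kinetics AUC0-∞ = Dose/CL, which depends on dose but not on infusion duration. With one compartment, C_EOI = (Dose/T)/CL × (1 − e^(−kT)), where T is the infusion duration; it depends on both. CL, Vss and t1/2 depend on neither. So Cohort 4 mixes AUC0-∞ and C_EOI, and Cohorts 2 and 3 mix C_EOI and Tmax only.

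**Cohort 4: location.** Inputs: 50% of 8 = 4 subjects at 10 mg/kg and 4 at 15 mg/kg, 60 minutes for all, cilastatin 1:1 with imipenem. The dose ratio is 1.5. The 500 mg cap binds only above 500/15 = 33.3 kg, so it is taken not to matter below 2 years of age.

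| Pooled summary | Relative to 10 mg/kg | Relative to 15 mg/kg |
|---|---|---|
| Geometric mean | √1.5 = 1.225 (+22%) | 1.225/1.5 = 0.816 (−18%) |
| Arithmetic mean | (1 + 1.5)/2 = 1.25 (+25%) | 1.25/1.5 = 0.833 (−17%) |

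No half-life is needed, because T is the same in both halves.

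**Cohort 4: spread.** The documents give no CV for cilastatin, so 30–50% is assumed (the adult imipenem CL figure in Section 8.9 is 50%). On the log scale the true variance is ln(1 + CV²). The dose mix adds (ln 1.5/2)² = 0.0411, or 0.0411 × 8/7 = 0.0470 with the n − 1 divisor for n = 8. The apparent CV is √(e^v − 1), where v is the sum.

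| Assumed true CV | ln(1 + CV²) | v | Apparent CV |
|---|---|---|---|
| 30% | 0.0862 | 0.127–0.133 | 37–38% |
| 40% | 0.1484 | 0.190–0.195 | 46% (0.457–0.465) |
| 50% | 0.2231 | 0.264–0.270 | 55–56% |

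The arithmetic-scale mixture formula √[((1 + r²)/2)(1 + CV²)/((1 + r)/2)² − 1], with r = 1.5, gives 36.6%, 45.4% and 54.8%.

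**Cohorts 2 and 3: C_EOI.** Inputs: three subjects at 30 minutes and three at 60 minutes per cohort, same mg/kg dose. Section 4.2.2.3 gives a half-life of about 30 to 60 minutes for imipenem and relebactam; none is given for cilastatin, so 0.5–1 h is an assumption. At fixed dose C_EOI ∝ (1 − e^(−kT))/(kT). Let r be the 60-minute value divided by the 30-minute value. The pooled arithmetic mean is (1 + r)/2 times the 30-minute mean and (1 + r)/(2r) times the 60-minute mean.

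| Assumed t1/2 | r | Pooled vs 60 min | Pooled vs 30 min | Fall over 10 min, 1 − e^(−k/6) |
|---|---|---|---|---|
| 0.5 h | 0.750 | +16.7% | −12.5% | 20.6% |
| 0.75 h | 0.815 | +11.4% | −9.3% | 14.3% |
| 1 h | 0.854 | +8.6% | −7.3% | 10.9% |

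The last column is the fall allowed by the sampling rule itself, since the sample is "collected within 10 minutes after the end of study drug infusion". The pooling effect here is of the same order as, or smaller than, the looseness of the sampling window. Cohort 4 is the main case.

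**The case against.** The strongest case against acting is that little depends on these tables. Cilastatin has no target and no hypothesis, and it lies outside the population model. CL can properly be pooled and appears in the same summary, so AUC at either dose follows from dose/CL. That is true, and it limits the harm to reporting. It does not make the pooled AUC0-∞ and C_EOI readable.

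Grouping by age cohort does not forbid sub-rows, and Section 8.6.1 promises a Modeling and Simulation Analysis Plan before database lock. But that plan is introduced in connection with the relebactam and imipenem model and is not said to cover the cilastatin tables. Section 8.0 rules out a separate SAP. The only layout stated is by cohort.

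The Cohort 4 figures assume dose-proportionality for cilastatin, equal mean clearance in the two halves and an evaluable 4/4 split. Section 4.1.2.2 states proportionality for relebactam only. The halves are sequential in a cohort where renal maturation matters: the Appendix 12.3 entry thresholds across these ages run from 47 to 76 mL/min/1.73 m². Replacement is also allowed. These caveats stand. They affect the exact size, not the fact that two doses are pooled.

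Small cells are a fair objection. At an assumed CV of 40%, a normal-theory 95% interval for a mean is about ±33% with n = 8 (2.365 × 0.40/√8) and ±64% with n = 4 (3.182 × 0.40/√4). Individual values must therefore carry most of the information.

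Finally, the adverse-event layout is a precedent for splitting by dose, hence for Cohort 4 only. It says nothing about infusion duration.

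**Conclusion.** The concern holds. Followed as written, the plan yields a Cohort 4 cilastatin AUC0-∞ and C_EOI that match no regimen given: geometric mean 22% above the lower dose and 18% below the higher, with a spread that includes the dose difference. This rests on dose-proportional cilastatin kinetics, similar clearance in the two halves and the planned 4/4 split.

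The Cohorts 2 and 3 effect is confined to C_EOI and Tmax, depends on an assumed half-life and is secondary; AUC0-∞ there is not distorted under linear kinetics. The 3/3 splits are as planned: Section 5.2.1.2.1 reports 18 PK-evaluable subjects of 19 treated in Cohorts 1 to 3. Cohort 5 is affected only if its regimen is modified. Cohort 1 cannot be classified until the two statements of its infusion duration agree.

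The point should be corrected because the summary serves the primary objective. It does not threaten target attainment or dose selection.

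**What to change.** In Sections 8.1 and 8.6.1, replace the cilastatin sentence with wording such as:

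> Cilastatin AUC0-∞, C_EOI and Tmax will be summarised by age cohort and regimen received (dose and infusion duration), using the actual dose and recorded infusion times, with individual values listed. CL, Vss and t1/2 will be summarised by age cohort.

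Dose-normalised AUC0-∞ and C_EOI by cohort may be added. Using the actual dose also covers older children whose weight brings the 500 mg cap into play.

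Two points need settling alongside this:

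- Sections 5.2.1.2.1 and 5.2.2 must be reconciled on the Cohort 1 infusion duration after its interim review, before regimen groups are fixed.
- Tmax is a cilastatin parameter in Section 7.1.3.2 but not in Section 8.4.1; the two lists should agree.

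The cost is SAP wording in two places, the alignment of those sections and a few table rows. No new data are needed. Cells will hold three or four subjects, which is why the individual listing is part of the change. It should be done before database lock.

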### **8.6.2 Statistical Methods for Safety Analyses**

Safety and tolerability will be assessed by clinical review of all relevant parameters including the incidence, severity, and type of AEs, changes in clinical laboratory tests, and changes from baseline in vital sign measurements at the interim reviews and the end of study.

The type and incidence of all AEs and serious adverse events (SAEs) will be tabulated for each age cohort and dose level. The broad clinical and laboratory AE categories consisting of the percentage of subjects with any AE, a drug-related AE, an SAE, a drug-related SAE, and who discontinued due to an AE, as well as the most frequently occurring individual AEs will be summarized in the same manner. Special attention will be given to local tolerability events occurring at time of study drug administration and to those subjects who discontinue due to

an AE or an SAE. Descriptive and/or summary statistics for the raw laboratory safety tests, vital sign measurements, and/or changes from baseline may also be computed, as deemed clinically appropriate.

## **8.7 Interim Reviews for Potential Dose Adjustment**

Interim reviews of PK and safety data will occur at 3 stages in the study. First, interim reviews were performed for each of Cohorts 1 through 3 in this study when data from 50% (3 subjects) of subjects were available from a specific cohort. Second, an interim review of complete aggregated PK data from Cohorts 1 through 3 was performed prior to enrollment of Cohorts 4 and 5. Third, interim reviews for each of Cohorts 4 and 5 will be performed when data from 50% of subjects are available from a specific cohort. Results will be reviewed by an internal team. During the first and third interim reviews, the suitability of the initial dose for each age cohort will be assessed and a dose modification may be suggested for the remaining 50% of subjects in that cohort, as described in Section 5.2.1.2 – Dose Modification. The dose modifications that occurred as a result of the completed interim reviews are described in Section 5.2.1.2.1.

## **8.8 Multiplicity**

Because there are no pre-specified hypotheses, no adjustments for multiplicity will be made.

## **8.9 Sample Size and Power Calculations**

The proposed number of study participants by pediatric subset includes the following:

- Cohort 1 (age 12 to <18 years); at least 6 subjects
- Cohort 2 (6 to <12 years); at least 6 subjects
- Cohort 3 (2 to <6 years); at least 6 subjects
- Cohort 4 (3 months to <2 years); at least 8 subjects, at least 4 of whom are <1 year of age
- Cohort 5 (birth to <3 months); at least 18 subjects with at least 6 younger neonates (<1 week age), at least 6 older neonates (1 to <4 weeks age), and at least 6 infants (4 weeks to <3 months)

A simulation-based methodology was implemented in order to determine the appropriate sample size for each pediatric age cohort that would have at least 80% probability to achieve reasonable precision, defined as the 95% confidence interval within 60% to 140% of the population mean (approximately  $\leq 20\%$  RSE [relative standard error]), in the model-based estimation of primary PK parameters for both REL and imipenem in each pediatric age cohort. Variability in primary PK parameters was assumed to be the same as that estimated in adults based on the adult population PK model (coefficient of variation (%CV) for imipenem: 50% for CL, 75% for  $V_c$ ; %CV for REL: 40% for CL, 50% for  $V_c$ ).

The proposed trial design, in terms of sample sizes combined with the PK sampling scheme, was found to be sufficient to have >80% probability (based on replicate simulations) to

achieve the defined target precision in model-based primary PK parameter estimates (CL, Vc) for both REL and imipenem, and thus, is expected to adequately capture the PK characterization for both drugs in the pediatric population.

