1. The interim review revealed a suboptimal (ie, too high or too low) initial dose based on inadequate (ie, too high or too low) PK target attainment relative to adults for a given age cohort (details in Section 5.2.1.2 – Dose Modification), or
2. The safety profile was not acceptable.

Dose modifications following the interim reviews in Cohorts 1 through 3 are described in Section 5.2.1.2.1.

When enrollment of all 6 subjects each in Cohorts 1, 2, and 3 was completed, a second interim review was performed in which aggregated data from Cohorts 1, 2, and 3 was used to (1) develop and refine a pediatric population PK model and conduct simulations to evaluate PK target attainment, and (2) assess whether the safety profile was acceptable for each age cohort. The findings from the second interim review were used to inform the proposed initial doses for Cohorts 4 and 5, which is 10/5 mg/kg IMI/REL. Subject enrollment of Cohorts 4 and 5 was initiated in parallel.

For Cohorts 4 and 5, an interim review will be conducted in each age cohort after the first 4 (50%) subjects are enrolled in Cohort 4 and the first 9 (50%) subjects are enrolled in Cohort 5 (regardless of subcohort), at which point, enrollment in that cohort will pause.

Enrollment will continue past the fourth subject in Cohort 4 and the ninth subject in Cohort 5 without dose modification if the following occurs:

1. The interim review demonstrates that the selected initial dose is suitable based on PK target attainment that is similar to that in adults for a given age cohort (details in Section 5.2.1.2 – Dose Modification), and
2. The dose demonstrates an acceptable safety profile in the exposed cohort, as described in Section 5.2.1.2 – Dose Modification.

Alternatively, enrollment in each cohort will continue with a dose modification based on Section 5.2.1.2 – Dose Modification if the following occurs:

1. The interim review reveals a suboptimal (too high or too low) initial dose based on inadequate (too high or too low) PK target attainment relative to adults for a given age cohort (details in Section 5.2.1.2 – Dose Modification), or
2. The safety profile is not acceptable.

When enrollment into Cohorts 4 and 5 has been completed, a final analysis of PK and safety data will be performed with aggregated data from Cohorts 1 through 5 to refine the optimal dosing for pediatric subjects based on PK target attainment and an acceptable safety profile.

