As treatment options are limited for MDR infections, and given that there are fewer antibiotics approved for use in pediatric patients as well as the dearth of clinical trials conducted in pediatric patients, the problem is even more critically important to address [9]. Carbapenems are the mainstay of treatment of MDR Gram-negative infections; therefore, the emergence of carbapenem-resistant organisms in recent years is particularly worrisome [10]. The addition of REL to IMI to restore IMI susceptibility for pathogens that produce class A and C  $\beta$ -lactamases therefore addresses an area of growing unmet medical need. Furthermore, IMI/REL is unique among  $\beta$ -lactam/BLI combinations in development due to the long history of pediatric safety and efficacy (Section 4.1.4 – Imipenem/Cilastatin Clinical Experience in Pediatric Populations) and the broad spectrum of activity of the  $\beta$ -lactam compound.

The current United States (US) Food and Drug Administration guidance document for pediatric PK studies focuses on appropriate dosing in the pediatric population based on PK data [11]. The PK of a drug in the pediatric population usually cannot be precisely predicted from PK or clinical studies of adult subjects; rather, specific PK studies in pediatric subjects are needed to determine appropriate pediatric dosing. Thus, the current study will be conducted to investigate the PK and safety of a single IV dose of IMI/REL in pediatric subjects from birth to <18 years of age receiving standard-of-care antibacterials for treatment of confirmed or suspected Gram-negative bacterial infection. The current study will be conducted using 5 age cohorts, with the predominance of subjects in the youngest age cohort, in accordance with guidance from the Food and Drug Administration and the European Medicines Agency (EMA). The information from this study will be used to determine appropriate dosing regimens for a subsequent efficacy study of IMI/REL in a pediatric population.

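### Does Section 8.9 overstate the precision for imipenem central volume in Cohorts 1 to 4, which have only 6 or 8 children each?

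*Combined protocol and SAP*

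**What the plan says.** Section 8.9 defines its target as "at least 80% probability to achieve reasonable precision, defined as the 95% confidence interval within 60% to 140% of the population mean", which it equates with an RSE of about 20% or less. The target applies "in the model-based estimation of primary PK parameters for both REL and imipenem in each pediatric age cohort". Variability is taken from the adult model: "coefficient of variation (%CV) for imipenem: 50% for CL, 75% for" Vc; for relebactam (REL), 40% for CL and 50% for Vc. Cohorts 1 to 3 have at least 6 subjects each, Cohort 4 at least 8 and Cohort 5 at least 18. The design "was found to be sufficient to have >80% probability (based on replicate simulations) to" reach that target for CL and Vc of both drugs. The summary in Section 8.1 labels the sample size "Based on PK Precision".

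The analysis itself is set out elsewhere. Section 8.6.1 builds a nonlinear mixed effects model "by using previous adult data in the form of the adult population PK model" and updates it as each cohort reports. Section 8.4.1 asks for CL and Vc as model-based population means. Section 2.1 says that, once Cohorts 4 and 5 are enrolled, "a final analysis of PK and safety data will be performed with aggregated data from Cohorts 1 through 5". Section 5.2.1.2.1 reports that an allometrically scaled adult model described the Cohort 1 to 3 concentrations adequately, and that a single pediatric model was then built from 18 evaluable subjects.

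**The concern.** The precision target is worded cohort by cohort, and four of the five cohorts are very small. A parameter with a 75% CV cannot be estimated to 20% RSE from 6 or 8 children, however well each child is measured. So the claim of more than 80% looks impossible for imipenem Vc in Cohorts 1 to 4, and doubtful for imipenem CL and REL Vc in Cohorts 1 to 3.

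It could hold in every cohort only if typical values are shared across cohorts or with adults, and Section 8.9 does not describe any such sharing. It is also the only quantitative support for the cohort sizes. A reader might conclude either that the figure is wrong or that each cohort's parameters rest on its own children when they do not.

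**Working it through.** **Inputs.** CVs, cohort sizes and the target come from Section 8.9. The target is consistent with itself: a half-width of 40% gives 0.40/1.96 = 20.4%, or about 20% RSE. The reported probability cannot be reproduced exactly, because the structural model, the residual error and the sharing used in the simulation are not given. What can be done is to bracket it.

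**Step 1: each cohort alone.** Treat every child's parameter as known without error. This is a best case, since three postdose samples and assay noise can only widen the intervals. Then RSE = CV/√n.

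| CV | n = 6 | n = 8 | n = 18 |
|---|---|---|---|
| 75% (imipenem Vc) | 30.6% | 26.5% | 17.7% |
| 50% (imipenem CL, REL Vc) | 20.4% | 17.7% | 11.8% |
| 40% (REL CL) | 16.3% | 14.1% | 9.4% |

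The probability that the estimated RSE is 20% or less was simulated from lognormal samples. The log-scale SD was set either to √ln(1+CV²) or to the CV itself, and the RSE was computed on the log or the arithmetic scale. The ranges span those choices.

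| CV | n = 6 | n = 8 | n = 18 |
|---|---|---|---|
| 75% | 17–31% | 22–40% | 70–95% |
| 50% | 56–66% | 74–81% | 99–100% |
| 40% | 81–85% | 93–97% | 100% |

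Using a maximum-likelihood SD (divisor n) lifts imipenem Vc in Cohorts 1 to 4 to no more than 43%. Sharing only the variance does not help: a cohort-specific typical Vc still has an RSE of 0.75/√6 = 30.6%.

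**Step 2: the model the plan describes.** Suppose one scaled typical imipenem Vc is shared.

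- All 44 subjects: 0.75/√44 = 11.3%. The probability of an RSE of 20% or less is about 98–100%. On the strictest reading, a t-based interval lying inside 60–140% of the true mean, it is 82–90%.
- Cohorts 1 to 3 only, n = 18: 17.7%, with probability 81–95% on the log scale and 70–85% on the arithmetic scale. No adult data are used here.

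**Step 3: partial sharing.** Let τ be the SD of the differences between cohorts that remain after scaling. This is an assumption; the documents give no value. With s² = CV² or ln(1+CV²), and W = Σ 1/(τ² + s²/nⱼ) over the other four cohorts, the variance for a cohort of size n is 1/[n/s² + 1/(1/W + τ²)]. For imipenem Vc in a cohort of 6:

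| τ | RSE |
|---|---|
| 0 | 10–11% |
| 0.10 | 14–15% |
| 0.20 | 18.5–19.7% |
| 0.30 | 22–23% |
| no sharing | 27–31% |

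Even without adult data, an expected RSE of 20% is reached if cohorts differ by up to about 20% after scaling. Adult information, which Section 8.6.1 brings in, would reduce these values further.

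**The case for a change.** The strongest case for a change is that the whole claim rests on an unstated assumption. Section 4.2.1 itself warns: "The PK of a drug in the pediatric population usually cannot be precisely predicted from PK or clinical studies of adult subjects". Section 5.2.1.2.1 adds a renal-maturation adjustment to carry the model below 2 years of age. No passage links the models in Sections 5.2.1.2.1 and 8.6.1 to the simulation in Section 8.9, and the Modeling and Simulation Analysis Plan promised in Section 8.6.1 is not said to cover sample size. A reader cannot tell how much of a cohort's precision comes from its own children.

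That last point stands: Section 8.9 would be clearer if it named what was shared. The rest carries less weight. The maturation adjustment concerns elimination, so it bears on CL, not on Vc, where the shortfall is largest. The warning in Section 4.2.1 is general, whereas the trial's own interim reviews found that the scaled adult model fitted Cohorts 1 to 3. Section 8.9 also says its target is for model-based estimation, which points to the population model and not to separate cohort means.

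**Conclusion.** No change to the plan follows. The cohort-only arithmetic is right, but it tests an estimator that the plan does not use. Under the pooled population model the reported probability of more than 80% is attainable for imipenem Vc, the most demanding parameter (RSE 11.3% with one shared value), so no stated figure is shown to be false.

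What remains is a gap in description. An analyst following Sections 2.1, 8.4.1 and 8.6.1 would fit the same model and run the same simulations whether or not Section 8.9 named the shared parameters. No dose decision uses a cohort-only interval for Vc, and no hypothesis is tested. Enrolment in Cohorts 1 to 4, where the shortfall would lie, is complete, and the fitted model will provide the actual standard errors.

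This conclusion assumes that the simulation behind Section 8.9 used the kind of model described elsewhere in the plan, and that scaled typical volumes differ between cohorts by no more than about 20%, or that adult data make up the difference. The documents do not confirm either assumption, but nothing in them contradicts either. The calculations ignore residual error and sparse sampling, so they are best cases for the pooled and cohort-only readings alike.
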